3.3.1 Research Subjects

- Patients who, in the opinion of the investigator or the patient's neurologist, are unable to give Informed Consent due to mental impairment or any other reason AND do not have a LAR who can give Informed Consent on their behalf. Patients aged 12-17 (inclusive) must provide assent if they are mentally capable of doing so, and must also have a caregiver who provides Informed Consent on their behalf
- Patients who, in the opinion of their neurologist at the University of Pennsylvania, are not good candidates for donating blood for any reason

3.3.2 Control Subjects

- Younger than 18
- Experience seizures or suspected seizures of any type (a single instance of febrile seizure prior to age 2 is allowed)
- Treatment with an anti-seizure medication within two months prior to providing a blood sample
- Unable to provide Informed Consent

3.4 **Recruitment**

Before the research begins, the Principal Investigator will present this study to the University of Pennsylvania's Neurology Department's Patient-Oriented Research Committee.

The study team will also present the study to the attending epileptologists, resident physicians, fellows, and nurse practitioners at the Penn Epilepsy Center and ask for their advance permission to contact their new patients in the outpatient clinic, and their patients who are admitted to HUP for cVEEG monitoring. Physicians who object to the study for any reason may elect not to allow their patients to participate. Physicians and nurse practitioners may also elect to contact the study team to prohibit them from inviting individual patients to join for any reason, or to prohibit enrolled subjects from giving blood. All Research Subjects who join the study at their first outpatient visit may provide a blood sample in support of Specific Aim 1, regardless of when the blood draw occurs – at their first visit or at a later visit – since they will have been prospectively identified and enrolled as part of a true cohort.

In the interest of enrolling a true cohort and in consideration of the low-risk nature of this study, in the absence of an attending physician's objection, the study team may approach all potentially eligible patients (provided that the physician has previously approved the study as described above).

The study team will review clinic lists and identify patients who are attending new outpatient visits at the Penn Epilepsy Center or are being admitted for cVEEG monitoring. A member of the study team may approach and consent any potential subject in the outpatient setting at any point during their visit. The study team may approach any potential subject who has been admitted for cVEEG monitoring at any point after his or her admission.

The study team will invite adults who accompany Research Subjects to participate as Control Subjects as time permits until a maximum of 240 Control Subjects have provided a single blood sample.

3.5 Informed Consent

No blood sample or medical information may be collected prior to or in absence of a subject or subject's LAR giving Informed Consent.

To begin the informed consent process, an appropriately trained member of the study team, such as the Principal Investigator, Sub-Investigator, Study Coordinator, or Research Assistant, will approach potential subjects in a private area and explain the overall study and the consent document using language that the individual can easily understand. The study team will make every effort to complete the informed consent process in a private room, but when space constraints render this impossible and potential subjects do not object, the study team may complete the informed consent process in a semi-private alcove space in the outpatient clinic normally. When all of the potential subject's questions have been answered to his or her satisfaction, he or she will be invited to sign the Informed Consent form. All subjects will receive a copy of the signed document. Original signed Informed Consent forms will be kept in the study files, in a locked office at the Penn Epilepsy Center. This process applies to both Research and Control Subjects.

3.6 Withdraw

If a Research or Control subject informs the research team either by phone or mail of his or her desire to withdraw from the study and the subject's sample or samples have not already been used for research, that subject's samples will be destroyed as outlined in the Informed Consent form. This decision will not affect results from research already performed on the subject's samples, but no additional tests will be carried out and the study team will not access his or her medical record after notification of withdraw.

4 Risk Analysis

An appropriately trained individual will draw a single sample of approximately 5ml of blood by venipuncture no more than twice per day. Risks of venipuncture include discomfort, bruising, dizziness, and rarely fainting and infection.

The greatest risk associated with this study is the release of health records. In addition to following all HIPAA guidelines, the study team will take extensive steps to minimize this risk, as described below in Section 9, "Sample Processing and Storage," and Section 10, "Privacy and Confidentiality."

5 Safety and Adverse Events

All adverse events will be collected and reported in accordance with International Conference on Harmonization and Good Clinical Practice Guidelines.

5.1 Definitions

Adverse Event

An adverse event (AE) is any symptom, sign, illness or experience that develops or worsens in severity during the course of the study. A preexisting condition should only be considered an AE if it increases in frequency or intensity during the study.

Serious Adverse Event

A serious adverse event (SAE) is an AE that results in any of the following outcomes:

- Death
- Life-threatening
- Hospitalization or prolongation of hospitalization
- Congenital anomaly or birth defect
- Persistent or significant disability or incapacity
- Important medical event (in the investigator's judgment, the event jeopardizes the subject's health, or required intervention to prevent another serious outcome listed above)

Unanticipated Problems Involving Risk to Subjects or Others

Any incident, experience, or outcome that meets all of the following criteria:

- Unexpected in nature, severity, or frequency (i.e. not described in study-related documents)
- Related or possibly related to participation in the research (i.e. there is a reasonable possibility that the research procedures may have caused the incident experience, or outcome)
- Places subjects or others at greater risk of physical, psychological, economic, or social harm

5.2 Recording and Reporting Adverse Events

Because this is not an interventional study, AE recording and reporting will be limited to AEs that may be related to study procedures (i.e., blood draws). All AEs that occur from the time that subjects sign informed consent through their completion of the research blood draws will be collected and reported.

Study staff must actively seek information about adverse events and unanticipated problems involving risk to subjects or others. Adverse events must be recorded in the case report form (CRF).

The clinical course of each AE must be followed until resolution, stabilization, or the investigator's determination that study participation did not cause the AE. SAEs that are ongoing at the end of the study must be followed through final outcome. Any SAE that occurs after a research blood draw and is considered to be possibly related to the study should be recorded and reported immediately.

All SAEs must be reported to Cognizance Biomarkers as soon as possible, but no later 24 hours after the study staff becomes aware of the event. The event should be reported using Cognizance Biomarkers' SAE report form, and include all readily available information. Follow-up reports must be issued as new

information about the SAE becomes available. Additionally, study staff must follow institutional requirements for reporting AEs, SAEs, and unanticipated problems involving risks to subjects and others.

5.3 *Medical Monitoring*

Cognizance Biomarkers will monitor the study progress on-site at periodic intervals throughout the study. This will include careful assessment and appropriate reporting of adverse events as noted above.

6 Data Handling

6.1 *Research Subjects*

Source documentation of subjects' medical history, clinical epilepsy diagnostic procedures, and epilepsy medications will remain in subjects' medical charts. Signed Informed Consent/ HIPPA forms will be stored in separate study binders. The only study procedures associated with this research are blood draws; all other data used for the study will be extracted from subjects' medical records and recorded on the CRFs.

6.2 *Control Subjects*

Data will be limited to the following, and will be self-reported at the time of Consent:

- Gender
- Age
- Confirmation that they do not experience seizure or suspected seizures
- Confirmation that they are not being treated with anti-seizure medications for any condition

All data will be stored in study binders, separate from signed Informed Consent/ HIPPA forms.

7 Data Analysis

7.1 *Sample Size Determination*

Enrollment will continue until 240 outpatients have joined the study, provided a single blood sample, and undergone an EEG that is accessible to the study team. Subjects who either do not provide a blood sample or do not undergo an EEG will be replaced.

This sample size is based on the need for 68 subjects per group and reflects the expectation that within six months of initial presentation, 50% will be diagnosed with epilepsy, 30% will be diagnosed with non-epileptic events, and 20% will have an unknown diagnosis.

Control samples will be used as needed to further validate the CARPE test.

7.2 *Statistical Methods*

The goals of the study are to determine whether the CARPE value can be used effectively and accurately to diagnose patients with epilepsy, and to establish the threshold for diagnosis. The CARPE AUC from

the ROC curve of our pilot data was 1.0 and the sICAM5 AUC was 0.87. For a conservative estimate, the sample size will be estimated based on the sICAM5 AUC, which is the lower value.

Accuracy: To determine the accuracy of the test, we will construct ROC curves for sensitivity and specificity of CARPE by varying the threshold value for classifying epilepsy patients. The gold standard for constructing the ROC curve will be the diagnosis as determined by the panel of three independent epileptologists. The aim of this part of the study is to construct a reliable ROC curve. It is likely that the gold standard panel will not come to a conclusive diagnosis approximately 20% of the time, and these unknowns will not be included in the ROC determination. We will consider a conclusive diagnosis to be agreement between at least two of the three epileptologists that the subject is epileptic or non-epileptic at the time of evaluation. We use the AUC of the ROC curve as a global measure of the effectiveness of these measurements. To this end, we assume that the prevalence rate is 50% for epilepsy among all the study subjects. Moreover, we assume that the CARPE and sICAM5 measures are normally distributed for both epilepsy and non-epilepsy subjects.

With an Alpha of 0.05 and a Beta of 0.2, comparing the AUC of 0.87 to the null hypothesis value of 0.7, the minimal required sample size per group is 68. The smaller group in this study will be subjects who have the diagnosis of non-epileptic attacks, which will likely represent 30% of the whole group. This justifies the sample size n=240 as adequate for the study. The determination of success will be based on this analysis.

Threshold: The second analysis will establish the threshold values to be used for the expected subsequent study. The goal is to choose the threshold value of CARPE for identifying epilepsy subjects with specificity of 0.8 and sensitivity of 0.8. For this analysis the entire study group will be analyzed. The panel of epileptologists will provide their best estimate of likely epileptic or likely non-epileptic events for this analysis (agreement among two members of the panel will be sufficient).

Our gold standard comparator in for this study is the panel of three independent epileptologists rather than EEG alone due to the fact that EEG's sensitivity for detecting epilepsy is only 50%.^{9,10} It is understood that CARPE must significantly exceed this in order to be considered a useful diagnostic test.

8 Sample Collection

- Outpatient Research and Control Subjects will be asked to provide up to two 5ml tubes of blood via venipuncture for research at enrollment. It will not be considered a violation if the Control Subject gives less than two tubes of blood (i.e., if he or she gives one tube or less, or if the phlebotomist is unable to obtain any amount of blood).
- Subjects who undergo cVEEG monitoring at HUP will be asked to provide no more than two 5ml sample of blood via venipuncture per day (12am-11:59pm) for research.
- All Research Subjects will have the option of providing an additional single 5ml sample of blood via venipuncture for research at any regularly scheduled clinic visit that takes place within 12 months of enrollment (Control Subjects will only be asked to give blood at the time of enrollment.)

All samples will be collected at the Hospital of the University of Pennsylvania's Department of Neurology.

All blood draws are optional, and it will not be considered a protocol deviation if a blood draw is missed for any reason (including subject preference).

9 Sample Processing and Storage

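### The stated minimum of 68 per group does not follow from the stated AUC test, which needs about 31–35 two-sided; the error is conservative and 240 remains adequate for that test at an AUC of 0.87

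*Combined protocol and SAP*

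**What the plan says.** The calculation is in section 7.2 (Accuracy). The design value is the pilot AUC of sICAM5 (0.87), chosen as conservative because the pilot AUC of CARPE was 1.0: "the sample size will be estimated based on the sICAM5 AUC, which is the lower value". The error rates are given as "With an Alpha of 0.05 and a Beta of 0.2", and the result is "comparing the AUC of 0.87 to the null hypothesis value of 0.7, the minimal required sample size per group is 68". For distributions, "we assume that the CARPE and sICAM5 measures are normally distributed for both epilepsy and non-epilepsy subjects".

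Section 7.1 carries the figure into the enrolment target: "This sample size is based on the need for 68 subjects per group". It expects 50% epilepsy, 30% non-epileptic events and 20% undetermined. Section 7.2 leaves the undetermined out of the ROC analysis, takes the non-epileptic 30% as the smaller group, and concludes: "This justifies the sample size n=240 as adequate for the study". It adds: "The determination of success will be based on this analysis".

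Neither section gives a formula, the sidedness of alpha, a variance method or the allocation behind 68.

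**The concern.** The wording describes a one-sample problem: an AUC estimated in this study, compared with a constant. The gap of 0.17 is large for such a test, and 68 per group looks about twice what 80% power requires.

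This matters because 68 is the only numerical basis given for 240. A reader cannot rebuild it from the stated inputs, and the text misdescribes the margin. Setting 72 expected non-epileptic subjects beside a minimum of 68 suggests little slack. If 28% rather than 30% were non-epileptic, 0.28 × 240 = 67 subjects would read as a shortfall, although 67 is more than twice what the stated test needs in the smaller group. What is at stake is the sample-size justification, not the conduct of the study.

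**Working it through.** **Inputs.** From section 7.2: null AUC 0.70, alternative 0.87 (difference 0.17), alpha 0.05, power 0.80, normality in both groups. From section 7.1: 50/30/20 of 240, that is 120 epilepsy, 72 non-epileptic and 48 undetermined. Assumed here because the plan is silent: sidedness (both tried) and the SD ratio, epilepsy to non-epilepsy (0.5 to 2).

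**The plan's own figures.** The step from 68 to 240 holds: 68/0.30 = 227, and 30% of 240 is 72. The 68 itself does not reproduce.

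**Required n for the stated test.** The condition is z_alpha × SE(0.70) + 0.8416 × SE(0.87) ≤ 0.17. With Hanley-McNeil variance and equal groups, n × variance ≈ V(A) = A/(2−A) + 2A²/(1+A) − 2A²:

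- V(0.70) = 0.5385 + 0.5765 − 0.98 = 0.1349, square root 0.3673.
- V(0.87) = 0.7699 + 0.8095 − 1.5138 = 0.0656, square root 0.2562.
- Two-sided: n = [(1.96 × 0.3673 + 0.8416 × 0.2562)/0.17]² = (0.9356/0.17)² = 30.3, so 31.
- One-sided (1.645): 23.3, so 24.

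At 5:3, with n the smaller group, V becomes [A/(2−A) − A²] + 0.6 × [2A²/(1+A) − A²], which is 0.1003 at 0.70 and 0.0446 at 0.87. Then n = [(1.96 × 0.3168 + 0.8416 × 0.2111)/0.17]² = 22.1, so 23.

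**Power.** Power = Φ[(0.17 − 1.96 × SE(0.70))/SE(0.87)]. At 68/68 the finite-sample Hanley-McNeil SEs are 0.0447 and 0.0312, which gives Φ(2.64) = 99.6%. At 120/72 they are 0.0374 and 0.0250, which gives Φ(3.87), above 99.9%.

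The same steps under other variance methods (power two-sided, true AUC 0.87):

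| Variance | n per group 1:1, two-sided | 1:1, one-sided | Smaller group at 5:3, two-sided | Power 68/68 | Power 120/72 |
|---|---|---|---|---|---|
| Hanley-McNeil | 31 | 24 | 23 | 99.6% | >99.9% |
| Exact binormal, SD ratio 1 | 31 | 24 | 25 | 99.7% | >99.9% |
| Exact binormal, SD ratio 0.5 | 34 | 26 | 31 | 99.3% | 99.7% |
| Exact binormal, SD ratio 2 | 34 | 26 | 23 | 99.3% | >99.9% |
| Obuchowski | 35 | 27 | 27 | 98.7% | 99.9% |
| Worst case, A(1−A)/smaller n | 49 | 38 | 49 | 93.3% | 94.7% |

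Using the null variance in both terms raises the two-sided 1:1 figures to 37–41, or 58 in the worst case. No variant reaches 68.

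**Total by the plan's 30% rule.** 23/0.30 = 77 and 31/0.30 = 104. The worst case gives 49/0.30 = 164. All are below 240.

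**Simulation check.** Normal data, logit-scale DeLong test, 10,000 runs, true AUC 0.87: 83.2% power at 31/31; 99.6% (SD ratio 1) and 98.7% (ratio 2) at 68/68; 99.96% (ratio 1) and 99.3% (ratio 0.5) at 120/72. At ratio 0.5 the simulated 99.3% is slightly below the closed-form 99.7%, so about 99% or more is the safe statement.

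**Two routes that do give 68.**

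- Two independent estimated ROC curves, two-sided, Hanley-McNeil: n = [(1.96 × √(2 × 0.1349) + 0.8416 × √(0.1349 + 0.0656))/0.17]² = 67.3, so 68. This depends on using the null variance for both curves in the alpha term; with V(0.70) + V(0.87) in both terms the result is 56.
- A total rather than a per-group figure: 2 × 34 = 68, with binormal SD ratio 0.5 or 2.

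**The case against.** The strongest reply is that nothing operational goes wrong. The figure errs on the safe side, the extra burden is blood draws only, and no analysis or decision rule uses 68. That stands, and it confines the point to documentation. It does not rescue the figure, because 68 is called a minimum for stated inputs that do not produce it.

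A second reply is that the plan leaves sidedness and variance open, so some convention might give 68. The table answers this: even the worst-case variance, which sets aside the plan's normality assumption, stays below 68.

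Four stronger readings are tempting, and the documents do not support them:

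- *The sponsor used a two-curve formula by mistake.* The match is exact, but so is 2 × 34, and the plan names no formula. The origin cannot be settled.
- *The success decision is compromised.* The sentence on determining success refers to the AUC analysis, not to the figure 68.
- *The plan presents 240 as only just sufficient.* It says adequate, and its expected smaller group (72) exceeds its stated minimum.
- *The required total is the 1:1 requirement divided by 0.30.* That applies equal-group figures to a design expected to split 5:3.

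**Conclusion.** The point holds as an error in the sample-size justification. The stated 68 is about twice the two-sided 1:1 requirement, or more than twice the smaller-group requirement at 5:3. Because the direction is conservative, 240 needs no change for the AUC test at a true AUC of 0.87. This rests on the plan's normality assumption, SD ratios between 0.5 and 2, and the expected 120/72 split.

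A reader might infer that 240 is thereby shown to be adequate for the whole study. It is not: the threshold analysis, with its targets of 0.8 for sensitivity and specificity, was not examined here. The result is also conditional on 0.87, which is a pilot value for sICAM5 rather than for CARPE.

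**What to change.** In sections 7.1 and 7.2:

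1. State that the test is one AUC against a fixed 0.70, and give the sidedness, variance method and allocation.
2. Replace 68 with the figure that follows from those choices; for example, 31 per group for two-sided alpha 0.05, 80% power, 1:1 groups and Hanley-McNeil variance. If 68 is kept for another reason, give it.
3. State what 240 delivers at the expected split: with 120 epilepsy and 72 non-epileptic subjects, two-sided alpha 0.05 and SD ratios from 0.5 to 2, power against 0.70 is about 99% or more if the true AUC is 0.87.

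The sponsor may add that the AUC detectable with 80% power at 120/72 is about 0.80–0.82 over the same SD ratios. That describes 240; it does not explain why 240 was chosen.

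The cost is wording only, with enrolment, the null value and the success criterion unchanged. The one drawback is that the corrected text will show 240 to be well above the roughly 77–104 that the stated test needs, so the sponsor should say why 240 is retained.

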9.1 Duration of Storage

Cognizance Biomarkers will store subjects' samples for approximately five years; this will allow ample time for batch processing and re-testing as necessary. We will destroy all samples that have not been processed after five years.

9.2 Vial Labeling

All samples collected for research will be de-identified and labeled with the date, protocol number, and a numerical or alphanumerical code. The samples will not include any subject identifiers.

9.3 Sample Preparation

As soon as possible after it is drawn, plasma will be isolated from whole blood and stored at -80°C. The plasma will be assayed using academic or commercial testing.

10 Privacy and Confidentiality

10.1 Study Samples

Only personnel authorized by the University of Pennsylvania's IRB and Cognizance Biomarkers will have direct access to the study samples and documents. Samples will be labeled with only the following information: date of collection, protocol number, and numerical or alphanumerical ID. Control Samples will be designated as such with the letter "C." Any subsequent vials used during research will also be free from personally identifying information and may only include, at most, the information listed above.

